**SA1. Community Advisory Board (CAB).** We will engage a CAB of 6-8 Mount Hope Cowboys (MHC) coaches and mothers to partner with us and guide decisions about intervention adaptation and refinement, including content and structure. Information will be solicited to guide the development of the in-person physical activity (PA) sessions (types of fitness activities, duration, etc.) before the intervention begins. Once underway, the CAB will provide input on issues related to intervention implementation and ideas for future refinement. Feedback will be provided via biweekly in-person or virtual meetings facilitated by Dr. [name] and a bilingual staff member. CAB meetings will be audio-recorded and detailed notes will be taken. CAB members will be incentivized \$200 (\$25 per meeting) for their time.

**SA2. Open Pilot Trial.** After modifying the intervention content and structure, we will then test it in an 8-week open pilot with a single group of 45 mothers (all receiving the intervention). The intervention will consist of in-person PA sessions (offered 3 times/week, with participants encouraged to participate at least twice), 2 goal setting sessions, and weekly written materials (e.g., brochures and tip sheets). Participants will complete 4 assessments (baseline, 4-weeks, 8-weeks (i.e., intervention end), and 1-month follow-up), the last of which will include an exit interview; 15 participants, chosen at random, will also be invited to complete an in-depth interview. Pre and post assessments and interviews will allow us to assess feasibility and acceptability (SA2a) and identify the potential impact of the intervention on mothers' PA (SA2b).

**Intervention Description.** While the final content and structure of the intervention will be informed by Specific Aim 1, participants will receive a culturally adapted, Social Cognitive Theory (SCT) and Transtheoretical Model- (TTM) based PA intervention. The evidence-based, theory guided aerobic PA intervention will systematically builds upon our prior studies and includes the following components: Goal setting. At baseline, participants will complete an in-person or Zoom goal-setting session based on motivational interviewing where they will learn about the benefits of MVPA, key behavior change techniques such as goal-setting and self-monitoring and establish personal PA goals. They will be assisted in developing a plan for gradually building up to 150 minutes of MVPA per week over 8 weeks and will discuss potential barriers and learn problem solving skills. Any participants already meeting the 150 min/week MVPA guideline will be assisted in developing a plan for sustaining their PA and achieving other PA goals. Midway through the intervention, participants will complete a second goal-setting session. In-person PA sessions. Participants will be invited to participate in PA sessions during their child's practice. Sessions will be offered 3 days/week, and participants will be encouraged to attend at least 2 sessions/week during the 8-week intervention. Sessions will last for 50 minutes, with the intention that attending all 3 sessions per week would allow participants to meet the recommended 150 minutes of MVPA per week. The time of the sessions (i.e., whether in the middle, first, or second of hour of practice) will be informed by the CAB, with all sessions including aerobic activities that encourage MVPA (jogging, jumping jacks, etc.). Participants will learn about proper form, movement techniques, safety, and injury prevention, and be given demonstrations on how to properly do each exercise using their own body weight or basic equipment that will be provided (e.g., resistance bands, jump ropes, small weights). Childcare, with age-appropriate movement activities, will provided for mothers with additional children not practicing. The PA equipment will be gifted to the MHC at the end of the intervention for continued use by mothers during practice. Written materials. Participants will be emailed brochures and tip sheets weekly throughout the intervention. Materials include motivation-matched PA manuals (based on baseline and week 4 assessments), tip sheets (on stretching, boredom, places to be active, etc.) and computer expert system-tailored PA feedback reports which draw from a bank of over 330 messages targeting different levels of SCT and TTM constructs (motivational readiness, self-efficacy, self-

regulation, processes of change, social support, outcome expectancies, and enjoyment for PA).

**Overview of Procedures.** Prior to the intervention, participants will be screened for eligibility, consented, and complete the baseline assessment. A goal-setting session will also be completed prior to beginning the in-person PA sessions and receiving print-based materials. Additional assessments will be conducted at 4-week (including a second goal setting session), 8-week (intervention end), and at 1-month follow-up. The purpose of the 1-month follow-up assessment is to see if the intervention has a sustained impact on parent PA (e.g., they continue to utilize the PA equipment and practice time to be active).

**Measures.** Assessments, conducted at practice, will be used to examine intervention feasibility, acceptability, and satisfaction, and effects, and to provide data for the tailoring expert system to function. Intervention feasibility, acceptability, usability, and satisfaction. Feasibility will be determined based on whether enrollment (i.e., 10-12 participants per week), retention (i.e.,  $>80\%$  of participants through 8 weeks), and assessment (i.e., obtain usable PA data from  $>80\%$  of participants) targets are achieved. Acceptability will be determined based on participant engagement with the intervention during the study period (i.e.,  $>80\%$  of participants attended at least 2 in-person sessions per week) and by assessing the degree to which participants find the intervention beneficial using Likert-type scales. Satisfaction will be assessed using an adapted version of the Consumer Satisfaction Measure, used by our research team in past trials and adapted for this study, and the Client Satisfaction Questionnaire. The intervention will be deemed satisfactory if  $>80\%$  of participants report a "good" acceptability or higher. Participants will complete an exit interview to assess the acceptability of the intervention components, duration, and structure. They will also be asked which components they found most/least helpful, whether they would recommend the intervention to others if offered again, and if they felt the intervention had an impact. Primary outcome for examining intervention effects on PA. Participants will complete a **7-Day PAR Interview** at each assessment (baseline, 4-weeks, at the end of the intervention, and at 1-month follow-up) to assess minutes of MVPA per week. This self-report instrument provides an estimate of total weekly minutes of MVPA and has been used across many studies. It has consistently demonstrated acceptable reliability, internal consistency, and congruent validity with other more objective PA measures along with sensitivity to changes in both moderate and intensive levels of PA. Our team has extensive experience with administering this instrument, which requires annual recertification. Potential moderators and mediators. **Demographics**, assessed at baseline, include age, education, income, race, marital status, employment and occupation, country of birth, and length of residence in U.S. Other potential moderators and mediators include SCT and TTM constructs, which will also be assessed for the purposes of tailoring print materials. **Stages of Change for Physical Activity** measure has successfully been used to stage-match treatment in our trials and has shown acceptable reliability (Kappa = 0.78; intraclass correlation  $r = 0.84$ ) and concurrent validity with measures of self-efficacy and current PA levels. **Processes of Change for Physical Activity (POC)** measure contains 10 subscales that address a variety of cognitive/behavioral processes related to PA behavior change. Internal consistency of the subscales range from .62 to .96. **Self-Efficacy For Physical Activity (SE)** measures self-efficacy to become physically active across diverse contexts. The internal consistency is acceptable ( $\alpha = .82$ ). **Social Support for Exercise (SSE)** has three subscales (Family, Friends, Rewards/ Punishments) and acceptable internal consistency ( $\alpha$ s .61-.91) and criterion validity. **Physical Activity Enjoyment Scale (PACES)** assesses level of personal satisfaction from PA. The measure has high internal

consistency ( $\alpha = 0.96$ ) and test-retest reliability. **Outcome Expectations Scale** assesses beliefs regarding the consequences of PA participation will be examined by 9 items with internal consistency ( $\alpha=.89$ ) and validity based on confirmatory factor analysis and positive correlations with PA and self-efficacy.

**Data Analysis.** [name], the study biostatistician, will provide guidance and oversee data analysis.

SA 2a. We will descriptively (means, proportions) analyze the post-intervention feasibility, acceptability, and satisfaction data. The qualitative exit interviews with participants will be audio recorded, transcribed, coded, and analyzed to determine how the intervention can be strengthened. The mixed methods findings will be used to refine the intervention content, structure, and assessments for future iterations of the intervention. SA 2b. Consistent with Aim 2b we will first examine within-person changes over time in PA outcomes (self-reported min/week of MVPA and a binary indicator of meeting national PA guidelines). Specifically, a longitudinal mixed effects model will regress min/week MVPA at end of treatment (8 weeks) and 1-month follow-up on baseline MVPA, time, and confounders identified a priori (e.g., age). Contrasts can be used to examine changes from baseline to 8 weeks in PA behavior, as well as changes 8 weeks to 1 month-follow up (to understand potential maintenance of behavior). Models will include a subject specific intercept to account for repeated measures within person over time. Next, a longitudinal model implemented with Generalized Estimating Equations with robust standard errors will be used to examine changes in meeting the national guideline of more than 150 min/week of MVPA over time controlling for baseline value of the indicator and potential confounders. This model will be specified to allow us to estimate whether the odds of meeting guidelines changed over time. In both cases (continuous and binary PA outcomes), interest is in estimating effect sizes rather than strict statistical hypothesis testing. Finally, a similar analytic strategy will be used to examine dose effects on both PA outcomes (by including a predictor in the model which counts the number of sessions attended/week). Models will be run using the fully enrolled sample under various assumptions of missing data and effects compared between models (for example, a multiple imputation approach vs. a likelihood-based approach to estimation).

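### As written, neither SA 2b model directly gives the change from baseline to 8 weeks, which is the effect estimate in this single-group pilot

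*Combined protocol and SAP*

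**What the plan says.** The section SA2. Open Pilot Trial describes one group of 45 mothers, all treated, and gives the purpose: "Pre and post assessments and interviews will allow us to assess feasibility and acceptability (SA2a) and identify the potential impact of the intervention". Under Measures, the 7-Day PAR is administered "at each assessment (baseline, 4-weeks, at the end of the intervention, and at 1-month follow-up) to assess minutes of MVPA per week".

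Under Data Analysis, SA 2b, the target for both PA outcomes is within-person change.

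- **Minutes of MVPA:** "a longitudinal mixed effects model will regress min/week MVPA at end of treatment (8 weeks) and 1-month follow-up on baseline MVPA, time, and confounders", with a subject-specific intercept. The plan continues: "Contrasts can be used to examine changes from baseline to 8 weeks in PA behavior". It also names the change from 8 weeks to 1 month, as a measure of maintenance.
- **Meeting the guideline:** a GEE with robust standard errors looks at change "over time controlling for baseline value of the indicator and potential confounders". It is to be specified so as to "estimate whether the odds of meeting guidelines changed over time". No outcome times and no reference time are given.

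For both outcomes the plan adds that "interest is in estimating effect sizes rather than strict statistical hypothesis testing".

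**The concern.** In a randomised trial, putting baseline on the right-hand side and follow-up visits on the left is standard, because the arm term carries the effect. Here there is no arm term. The effect has to come from comparing follow-up with baseline, and that comparison is lost from the time factor once baseline is only a covariate.

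For MVPA, the model sentence and the contrast sentence after it do not fit together. For the GEE, the one specification given, the baseline covariate, works against the stated aim. An analyst who follows the text could report a 1-month versus 8-week odds ratio as the intervention effect. An analyst who adds baseline rows to repair this, but keeps the covariate, would report an inflated odds ratio. Since the plan says its interest lies in effect sizes, this affects its main quantitative output.

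**Working it through.** **Inputs.** From the documents: n = 45, one group; 7-Day PAR at baseline, 4 weeks, 8 weeks and 1 month; the model terms quoted above. The documents give no rates, SDs, correlations or power calculation, so there is no stated figure to reproduce. All rates, SDs and correlations below are assumptions. The results in steps 1 and 4 about what each coefficient estimates do not depend on them; the sizes do.

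**1. MVPA: what the stated model estimates.** With B the baseline value and centred confounders,

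Y(i,t) = a + b·B(i) + d·[t = 1 month] + confounders + u(i) + e(i,t), for t = 8 weeks, 1 month.

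Time has two levels, so its only contrast is d, the change from 8 weeks to 1 month. The change from baseline to 8 weeks is a + b·mean(B) − mean(B), which is not a time contrast. In a simulated example (assumed true means 60/110/90 min/week, SD 70) the time coefficient was −18.8. The adjusted 8-week mean was 111.4 and the baseline mean 56.0, and 111.4 − 56.0 = 55.4, the paired change. The point estimate is therefore recoverable.

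**2. MVPA: the interval for the derived change.** Let k = SD at baseline / SD at 8 weeks, and r the correlation between them. The variance of the change is proportional to 1 + k² − 2rk. With the baseline mean treated as fixed it is proportional to 1 − r². The SE ratio is sqrt[(1 − r²)/(1 + k² − 2rk)]. For example, at k = 1 and r = 0.5 it is sqrt(0.75/1) = 0.87. Coverage of the nominal 95% interval comes from 20,000 simulated trials of n = 45 per cell:

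| k | SE ratio, r = 0.3 / 0.5 / 0.7 | Coverage (%), r = 0.3 / 0.5 / 0.7 |
|---|---|---|
| 0.6 | 0.95 / 0.99 / 0.99 | 93.9 / 95.0 / 94.6 |
| 0.8 | 0.89 / 0.94 / 0.99 | 91.6 / 93.3 / 94.7 |
| 1.0 | 0.81 / 0.87 / 0.92 | 88.8 / 91.1 / 93.0 |
| 1.2 | 0.73 / 0.78 / 0.82 | 84.9 / 87.6 / 89.2 |

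The plain paired change covers 94.6 to 95.1%.

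**3. MVPA with baseline on both sides.** With complete data this returns the paired mean change exactly (largest difference 6e-13 over 800 trials per r). With about 20% dropout concentrated at low baseline (logit slope −1.2 per baseline SD, SD 80, true change 90 min/week), its bias is −5.5, −4.1 and −2.3 min/week at r = 0.3, 0.5 and 0.7. With baseline as an outcome row only, the bias is −0.5, 0.0 and +0.2. The Monte Carlo SE is about 0.5.

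**4. GEE.** The true odds ratio at 20% to 60% is (0.6/0.4)/(0.2/0.8) = 6.0, and at 20% to 40% it is (0.4/0.6)/(0.2/0.8) = 2.67. Simulation: latent normal with equal correlations 0.3, 0.5, 0.7; logit link; exchangeable working correlation; no other covariates; very large n.

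| Rates: baseline / 8 wk / 1 mo | True OR, 8 wk vs baseline | Baseline as covariate only: time OR | Baseline on both sides: OR | Baseline as outcome row only: OR |
|---|---|---|---|---|
| 20/60/60 | 6.0 | 1.0 | 10.3, 17.0, 41 | 6.0 |
| 20/40/40 | 2.67 | 1.0 | 3.3, 3.9, 5.7 | 2.67 |
| 20/20/20 | 1.0 | about 1.0 | about 1.0 | about 1.0 |

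The covariate-only odds ratio compares follow-up visits with each other. At 20/60/50 it is 0.66, 0.65, 0.63, below 1 although the odds rose sixfold by week 8.

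The both-sides odds ratio is inflated because in the baseline rows the outcome equals the covariate. That drives the covariate's coefficient up, and an odds ratio conditional on so strong a predictor lies further from 1 than the marginal one. In the 60/110/90 example at correlation 0.5, adding baseline rows moved the baseline indicator's odds ratio from about 6 to about 23, and the 8-week time odds ratio was 5.5 against a marginal 3.7.

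**5. GEE at the trial's own size.** For n = 45, correlation 0.5, 20/60/60 and 2,000 trials, the median odds ratios were 1.00 (covariate only), 6.33 (outcome row only) and 17.0 (both sides, among estimable fits).

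**6. Recovery by standardisation.** Averaging the fitted 8-week probabilities over mothers and comparing them with the baseline proportion gives about 6.0 at 20/60/60.

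**The case against.** The strongest reply is that these are unstated steps rather than wrong models. The contrast sentence names the estimand, a biostatistician oversees the analysis, and with complete data both readings of the MVPA model lead to the right point estimate. The interval problem depends on an SD ratio the documents do not give: coverage falls below 91% in four of the 12 cells, all with the baseline SD at or above the 8-week SD. This stands as a limit on the MVPA half.

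For the GEE, the plan never uses the words versus baseline, says the model will be specified to serve the aim, and standardisation recovers the change. So the failure belongs to the time coefficient, not to everything that could be computed from the fit. That also stands. But an intention to specify is not a specification, and SA 2b sets within-person change as the target for both outcomes.

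The both-sides fit is not prescribed by the plan and often fails visibly at n = 45: in one rerun at 20/60/60, about 87%, 77% and 54% of fits were usable at correlations 0.3, 0.5 and 0.7. That lowers the chance of its being reported, but many fits would still pass unnoticed.

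Finally, the outcome-row GEE does not cure dropout bias. Under the same baseline-related dropout it gave 6.5, 6.8, 6.8 against a true 6.0, and the standardised covariate model gave 6.5, 6.9, 7.0. This is correct: for the GEE, neither remedy has a material advantage on dropout.

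**Conclusion.** The concern holds and should be fixed before analysis; it is not fatal. From the wording alone, the MVPA model's time factor cannot directly supply the promised change from baseline, and the GEE with its baseline covariate gives either a comparison among follow-up visits or an odds ratio inflated whenever there is a change.

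The MVPA consequence is modest: a recoverable point estimate, with an interval that ranges from adequate to clearly too narrow (95.0% down to 84.9% coverage over the assumed range). The GEE consequence can be large: 1.0, or 10.3 to 41, in place of 6.0 under the larger assumed effect; 1.0, or 3.3 to 5.7, in place of 2.67 under the smaller one. With no change there is no distortion. All these sizes rest on assumed rates, SDs and correlations.

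**What to change.** In both change-over-time models, make baseline an outcome row (baseline, 8 weeks, 1 month), use categorical time with baseline as reference, allow for within-person correlation, and drop the baseline-value covariate. Report 8 weeks versus baseline and 1 month versus 8 weeks. List the GEE's outcome times and say whether the 4-week assessment is used in either model.

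If baseline is kept as a covariate, state the derived contrast: the adjusted 8-week mean minus the baseline mean for MVPA, and the standardised 8-week probability against the baseline proportion for the guideline indicator. Obtain the interval by bootstrapping mothers, so that baseline sampling error is included. For the GEE this is an equally sound option.

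Under either option, baseline-related dropout in the GEE should be addressed through the missing-data comparison already planned, including multiple imputation. The dose models are not affected by this point.

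The cost is rewording two sentences. No new data are needed, since the same interview is already done at baseline.

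### Week-4 MVPA is scheduled for every participant but has no role in the continuous mixed model, so a woman who then misses both later visits adds nothing to the likelihood fit (minor, cheap to improve)

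*Combined protocol and SAP*

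**What the plan says.** SA2, Open Pilot Trial, sets the schedule for the single group of 45: "Participants will complete 4 assessments (baseline, 4-weeks, 8-weeks (i.e., intervention end), and 1-month follow-up". Overview of Procedures repeats it: "Additional assessments will be conducted at 4-week (including a second goal setting session), 8-week (intervention end), and at 1-month follow-up". Under the primary outcome in Measures, the 7-Day PAR is given "at each assessment (baseline, 4-weeks, at the end of the intervention, and at 1-month follow-up) to assess minutes of MVPA per week". Week-4 MVPA is therefore a planned measurement of the primary outcome on every participant.

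Data Analysis, SA 2b, specifies a mixed model with a random intercept per woman that will "regress min/week MVPA at end of treatment (8 weeks) and 1-month follow-up on baseline MVPA", together with time and confounders chosen in advance. The contrasts it names are baseline to 8 weeks and 8 weeks to 1 month. The GEE for guideline status lists no outcome times.

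On missing data the section says: "Models will be run using the fully enrolled sample under various assumptions of missing data". Its example is "a multiple imputation approach vs. a likelihood-based approach to estimation". It does not list the imputation variables. The retention target in Measures is more than 80% "of participants through 8 weeks".

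**The concern.** In a likelihood fit a participant counts only through her outcome rows. Here baseline is a covariate and the rows are 8 weeks and 1 month. A woman who attends baseline and week 4 but neither later visit has no row, so the likelihood fit does not use everyone enrolled.

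The loss of precision is slight. The risk that matters is bias. If less active women leave after week 4, and week-4 MVPA predicts week-8 MVPA beyond baseline and the confounders, the women left in the fit are too active and the 8-week estimate is too high. The measurements that would largely correct this have already been taken. The section says that "interest is in estimating effect sizes rather than strict statistical hypothesis testing", so an avoidable one-directional error in the effect size touches the purpose of SA 2b. No feasibility, acceptability or satisfaction target depends on this estimate.

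**Working it through.** The plan gives no precision or power figure for SA 2b, so there is nothing to reproduce.

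**From the documents.** 45 women. More than 80% of 45 is more than 36, so at least 37 must be kept (37/45 = 82.2%) and at most 8 lost: d = 8/45 = 0.178.

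**Assumed, not in the documents.** MVPA scaled to SD 1; correlation rho between visits of 0.3 to 0.7, either equal or decaying with distance, AR(1); all 8 losses after week 4 and missing both later visits; dropout odds x1.25 to x4 per SD lower week-4 MVPA.

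**Precision, loss at random.** Let r be the week-4/week-8 correlation given baseline. Adding week 4 multiplies the variance of the 8-week mean by 1 - r²d. Under equal correlation r = rho/(1 + rho).

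| rho | r | 1 - r²d | SE reduction |
|---|---|---|---|
| 0.3 | 0.231 | 0.9905 | 0.5% |
| 0.5 | 0.333 | 0.9802 | 1.0% |
| 0.7 | 0.412 | 0.9699 | 1.5% |

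**Bias of the planned fit.** Let g be how much higher the retained women were than the lost women at week 4, in SDs given baseline, and s the SD of week-8 MVPA given baseline. The retained mean exceeds the mean of all women by d times the gap between the groups, so bias ≈ d × g × r × s. The simulated column fits the planned random-intercept model in 700 trials per row. Dropout follows the baseline-adjusted week-4 residual with odds of about x2 (first row) or x4.5 (the others, slightly beyond the assumed range).

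| Correlation | g | r | s | d × g × r × s | Simulated |
|---|---|---|---|---|---|
| equal 0.3 | 0.74 | 0.231 | 0.954 | 0.029 | 0.030 |
| equal 0.5 | 1.25 | 0.333 | 0.866 | 0.064 | 0.059 |
| equal 0.7 | 1.23 | 0.412 | 0.714 | 0.064 | 0.061 |
| AR(1) 0.5 | 1.22 | 0.447 | 0.968 | 0.094 | 0.117 |
| AR(1) 0.7 | 1.23 | 0.573 | 0.872 | 0.109 | 0.112 |

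For AR(1), r = (rho - rho³)/√((1 - rho²)(1 - rho⁴)) and s = √(1 - rho⁴). At rho = 0.7 this gives 0.357/0.6225 = 0.573 and √0.7599 = 0.872. The 0.117 has a Monte Carlo error of 0.199/√700 = 0.0075 and lies above the formula, so I do not rely on it. The largest ratio of bias to SE in these runs was 0.69 (AR(1), rho 0.7).

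A larger simulation (4,000 trials per scenario) with dropout on the week-4 level gave +0.009 to +0.085 SD with 8 lost, +0.004 to +0.043 with 4 lost, and 0.00 at odds x1. Dropout on the baseline-adjusted residual, with odds up to x4, reached +0.106. The working range with 8 lost is therefore about 0.01 to 0.11 SD.

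**Does adding week 4 remove the bias?** It depends on how it is added:

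- Random intercept and common baseline slope: near zero under equal correlation, and near zero (-0.003 to +0.005) when dropout follows the week-4 level. With decaying correlation and dropout on week-4 change or residual (odds x2 to x4), about 0.013 to 0.040 SD remains.
- Baseline slope varying by time, still a random intercept: 0.008 to 0.028 SD remains in those cases.
- Imputing week 8 from baseline and week-4 MVPA: within about 0.007 SD of zero throughout. With baseline the only covariate and all losses after week 4, a likelihood fit with time-specific baseline slopes and unstructured covariance rests on the same regression of week 8 on baseline and week 4. It should therefore give the same point estimate.

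**Guideline status at 8 weeks** (as a proportion, 8 lost, dropout on the week-4 level, assumed cut-point 0.84 SD above the baseline mean, SD of the estimate about 0.08). GEE bias is +0.004 to +0.045; with week-4 rows added, +0.004 to +0.043; with imputation using week-4 MVPA, 0.000 to +0.002; with inverse-probability weights using it, -0.001 to +0.003. Extra rows alone do essentially nothing for the GEE.

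**What week 4 cannot repair.** If 4 of the 8 leave before week 4 for the same reason, +0.004 to +0.035 SD remains. If dropout follows unobserved week-8 activity, +0.020 to +0.194 SD falls only to +0.017 to +0.180.

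**The case against.** The model is coherent for the contrasts it names, neither of which involves week 4, and the Intervention Description gives the week-4 assessment another use, in matching the written materials. The plan promises several missing-data assumptions, and an imputation run could use week 4. Every size above is assumed, and the largest need steep dropout with all 8 permitted losses falling after week 4.

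Most of this stands, and it keeps the point minor. It does not remove it: no text reserves week-4 MVPA for tailoring, the named contrasts would be unchanged by adding week 4, and the imputation is offered only as an example with its variables unlisted.

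Three stronger readings are tempting but unsupported:

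- A reader might infer that anyone lost after week 4 drops out of the analysis. A woman who misses 8 weeks but returns at 1 month still has an outcome row.
- A reader might infer that week 4 is excluded from all of SA 2b, so that comparing imputation with likelihood would hide the bias. The plan neither includes nor excludes it from the imputation and is silent on the GEE's times.
- A reader might infer that adding week-4 rows to the planned random-intercept model cures the problem. Under decaying correlation it may only reduce it.

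**Conclusion.** The omission is real in the continuous model as written, and it conflicts with the stated use of all enrolled women for those who miss both later visits. It is a minor point. With 8 of 45 lost after week 4, the 8-week estimate is too high by about 0.01 to 0.11 SD on the assumed correlations and dropout odds. That is below one SE. It is zero if dropout is unrelated to week-4 MVPA, and smaller with fewer losses. The documents supply neither the correlations nor the dropout pattern, so this is a possible bias and not a demonstrated one. It would matter more if losses exceeded the target: with 14 lost, the simulated bias reached 0.80 SE.

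**What to change.** In the continuous model, add week 4 as a categorical outcome time (4 weeks, 8 weeks, 1 month), keep baseline as a covariate, and keep the 8-week contrast as the headline estimate. Let both the baseline slope and the residual covariance vary by time, for example unstructured; freeing the slopes alone is not enough.

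Name week-4 MVPA in the imputation model for the continuous and the binary outcome. For the GEE, rely on that imputation or on inverse-probability weights that use week-4 MVPA, and not on added week-4 rows alone.

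State that none of this corrects for losses before week 4 or for dropout driven by unobserved later activity.

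The cost is a few sentences in the analysis plan, a little analysis work, and a few more parameters to estimate with 45 women. No visit or measurement is added.

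### With 45 mothers, uncorrected robust GEE standard errors make the interval for the dose odds ratio mildly too narrow; the time contrasts are essentially unaffected

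*Combined protocol and SAP*

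**What the plan says.** Under SA 2b in Data Analysis, the binary outcome is "meeting the national guideline of more than 150 min/week of MVPA over time". It is to be modelled with "Generalized Estimating Equations with robust standard errors", "controlling for baseline value of the indicator and potential confounders". The same paragraph then states that "a similar analytic strategy will be used to examine dose effects on both PA outcomes", with weekly session attendance added as a predictor. The number of confounders is not given; age is the only example.

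The sample, under SA2 (Open Pilot Trial), is "a single group of 45 mothers". The Measures section sets a retention target above 80% "of participants through 8 weeks". On missing data, SA 2b says: "Models will be run using the fully enrolled sample under various assumptions of missing data", with multiple imputation and likelihood-based estimation as examples.

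The plan names no small-sample correction, reference distribution, working correlation or confidence level. It says that it wants effect sizes and not formal tests.

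**The concern.** The ordinary sandwich variance is built from each mother's residuals. The fitted model is pulled towards the data it is fitted to, so those residuals are on average too small. With few mothers the variance is therefore biased downward. The bias depends on leverage. It is largest for terms that differ only between mothers (dose, baseline status, age), because each mother counts once for these. It is smallest for time, where each mother is compared with herself.

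Because the plan aims to estimate, the interval carries the result. A dose interval that is too short overstates how much 45 mothers can say about attendance and meeting the guideline. The number of confounders is open, so the plan does not limit the problem.

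**Working it through.** **1. Figures in the plan.** There is no rate, effect size, interval width, alpha or power to reproduce. The only arithmetic is retention: 0.80 × 45 = 36, so a rate above 80% means at least 37 mothers (37/45 = 82%). The stated analysis set is all 45.

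**2. Formulas.** For mother *i*, let D be the derivative matrix, V the working covariance and r the residuals, with A = Σ D′V⁻¹D.
- Ordinary sandwich: A⁻¹ (Σ D′V⁻¹ r r′ V⁻¹D) A⁻¹.
- Leverage: H = D A⁻¹ D′V⁻¹.
- Kauermann-Carroll (KC) replaces r by (I − H)^(−1/2) r.
- Mancl-DeRouen (MD) replaces r by (I − H)⁻¹ r.
- Interval: estimate ± c × SE, with c = 1.96 (z) or the t quantile on *n* − *p* degrees of freedom. For *n* = 45 and *p* = 5 (intercept, time, baseline, one covariate, dose), t on 40 df is 2.021, and 2.021/1.96 = 1.031.

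**3. Simulation.** Logistic GEE with exchangeable working correlation and outcomes at 8 weeks and 1 month. The model has time, the baseline indicator, 1 or 3 covariates, and dose as one value per mother. There were 38 or 45 mothers and 4,000 replicates per scenario. Assumed, not in the documents: reference probability of meeting the guideline 20, 40 or 60%; 10 to 25% meeting it at baseline; latent correlation 0.6; dose symmetric (mean 2, SD 0.6) or skewed; dose log-odds 0 or 0.7; nominal level 95%. The code matched the ordinary and MD standard errors of a standard package to four decimals on one data set. Monte Carlo error is about √(0.93 × 0.07/4000) = 0.4 points.

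**4. Dose coefficient.** Coverage in % at 45 mothers, with width relative to the uncorrected z interval in brackets:

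| Rate, dose shape, covariates, log-odds | Uncorrected z | KC z | KC t | MD t |
|---|---|---|---|---|
| 60%, symmetric, 3, 0 | 93.0 | 95.1 (1.097) | 95.6 (1.133) | 97.4 (1.243) |
| 60%, skewed, 1, 0 | 93.6 | 95.0 (1.074) | 95.9 (1.107) | 96.9 (1.196) |
| 60%, skewed, 3, 0 | 93.0 | 95.0 (1.106) | 95.6 (1.142) | 97.4 (1.268) |
| 40%, symmetric, 1, 0.7 | 92.3 | 94.4 (1.064) | 95.3 (1.097) | 96.8 (1.169) |
| 40%, skewed, 1, 0.7 | 92.9 | 94.8 (1.072) | 95.5 (1.106) | 96.7 (1.191) |

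Over all scenarios, 38 and 45 mothers:
- Uncorrected z: 90.5 to 93.8%, worst with more covariates. At 90.5% the miss rate is 9.5% where 5% is intended.
- KC with z: 94.0 to 95.4%, 6 to 15% wider.
- KC with t: 94.8 to 96.2%.
- MD with z: 95.8 to 97.5%, 13 to 34% wider. MD with t: up to 98.4%, up to 40% wider.

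**5. Time contrasts.** Uncorrected coverage is 93.6 to 95.7% in the model with dose. Without dose, with 37, 38 or 45 mothers, it is 94.3 to 96.7%, whether baseline is a covariate or a third outcome time. KC or MD widens these intervals by 1 to 3%.

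**6. Other assumptions.** Two further simulations agree. One, with about 85 to 87% of 45 mothers seen, gave uncorrected dose coverage of 91.4 to 93.4% with one confounder and 90.3% with five. KC with t gave 95.2 to 96.1%, and time coverage was 93.4 to 95.5%. The other gave 91.9 to 93.9% uncorrected, 94.9 to 97.1% with KC and t, and 93.5 to 95.6% for time.

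**The case against.** The strongest case against has five parts.

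- **The plan does not say that the standard errors are uncorrected.** True: the wording does not exclude a corrected estimator, and a biostatistician oversees the analysis. But nothing calls for a correction, and the ordinary sandwich is the natural reading.
- **The model's purpose is change over time.** This stands. A reader might infer that all the GEE intervals are too narrow; the simulations do not support that. Minutes per week of activity are analysed with a mixed model, so this point does not touch them.
- **A correction is not free.** This stands. It needs no extra mothers or data, but the intervals widen. Nor will any correction do: MD with t can miss the nominal level by over 3 points in the other direction.
- **The standard error itself can look worse than it is.** In one set of runs the median robust SE was 0.79 to 0.84 of the sampling SD. A reader might infer a shortfall of 16 to 21%. With normal sampling that would give about 88 to 90% coverage (1.96 × 0.79 = 1.55; 1.96 × 0.84 = 1.65), below the 91.4 to 93.4% reported with one confounder. Near-separated fits probably inflate the SD, so coverage is the safer measure.
- **The planned analysis may use multiple imputation, which was not simulated.** This stands as a limit on the figures. Total variance is then W + (1 + 1/m)B. The sandwich enters through W, so its bias remains there, diluted by B.

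It is also fair that no decision rule depends on the dose odds ratio, and that the stated targets are feasibility, acceptability and satisfaction. That lowers the priority but does not correct the interval.

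**Conclusion.** The point holds for the dose odds ratio. Following the text as the ordinary sandwich gives nominal 95% intervals with about 90 to 94% coverage, and the shortfall grows with the number of covariates. KC restores coverage to about the nominal level. The time contrasts are essentially unaffected.

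The size rests on the assumed rates, correlation and dose distribution, on dose being one value per mother, and on 95% as the intended level. The dose model was run with 38 and 45 mothers, not at the floor of 37. The direction was the same in every set of assumptions tried. Priority is minor, because this is a secondary estimate in a single-arm pilot that aims to estimate.

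**What to change.** Add one sentence to SA 2b: GEE intervals, above all in the dose model, use the Kauermann-Carroll bias-corrected sandwich variance with t quantiles on mothers minus parameters (or z). Where multiple imputation is used, this variance is the within-imputation component. Name the working correlation, and fix a short list of confounders in advance. Do not list Mancl-DeRouen with t as an equivalent.

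Cost: no extra mothers or data. Dose intervals widen by about 6 to 15% from the variance correction, and somewhat more with t (10 to 14% in the tabulated scenarios with 45 mothers). Time intervals widen by about 1 to 3% from the variance correction, or 4 to 5% with KC and t at 45 mothers. The change does not cure sparse data or separation: up to 3.3% of simulated fits failed or diverged, so the plan should also say what is reported if the dose model does not fit.
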